2.8 Exclusion Criteria

- 2.8.1 Participants with progressive or refractory disease while receiving either a BTK inhibitor or PI3K inhibitor. Prior exposure to either a BTK inhibitor, PI3K inhibitor, or both is acceptable as long as the participant's disease did not progress during active therapy with the agent(s).
- 2.8.2 Participants who have undergone a major surgical procedure within 28 days of the first dose of study drug. If a participant had major surgery greater than 28 days prior to the first dose of study drug, they must have recovered adequately from any adverse event and/or complications from the intervention prior to the first dose (as judged by the treating investigator).
- 2.8.3 For enrollment to **Cohort 1**: For enrollment to Cohort 1: receipt of prior BTK inhibitor treatment or any other anti-cancer therapy (e.g. chemotherapy, immunotherapy, radiation, biologic therapy or any investigational agent) within five half-lives or 21 days, whichever is shorter, of the first dose of study drug.
- 2.8.4 Participants who are receiving any other investigational agents.
- 2.8.5 History of prior allogeneic stem cell transplant.

- 2.8.6 History of autologous hematologic stem cell transplant within 6 months of the first dose of study drug.
- 2.8.7 Participants with known Richter's transformation, or histological transformation from CLL to large cell lymphoma.
- 2.8.8 Participants with known CNS involvement, because of their poor prognosis and because they often develop progressive neurologic dysfunction that would confound the evaluation of neurologic and other adverse events. Participants with no known history of CNS leukemia are not required to undergo CT scan or lumbar puncture (LP) for trial eligibility unless the participant is symptomatic as judged by the treating investigator.
- 2.8.9 Participants with uncontrolled autoimmune hemolytic anemia (AIHA) or idiopathic thrombocytopenic purpura (ITP).
- 2.8.10 Participants with active clinically significant bleeding or history of bleeding diathesis (e.g., hemophilia or von Willebrand disease).
- 2.8.11 Participants requiring or receiving anticoagulation with warfarin or equivalent vitamin K antagonists (other anticoagulants are permitted).
- 2.8.12 Participants with a history of significant cerebrovascular disease/event within 6 months before the first dose of study drug, including stroke or intracranial hemorrhage.
- 2.8.13 Participants with uncontrolled intercurrent illness, including but not limited to: unstable angina pectoris, cardiac arrhythmia, or poorly controlled and clinically significant atherosclerotic vascular disease (including patients who required angioplasty, cardiac or vascular stenting within 6 months prior to the first dose of study agent), myocardial infarction within 6 months of screening, congestive heart failure, or patients with Class 3 or 4 cardiac disease as defined by the New York Heart Association Functional Classification (Appendix D). Note: participants with controlled, asymptomatic atrial fibrillation are permitted to enroll on study. Concomitant use of medication known to cause QT prolongation or torsades de pointes should be used with caution and at investigator discretion.
- 2.8.14 Individuals with a history of a different malignancy are ineligible with the following exceptions: individuals who have been treated and are disease-free for a minimum of 2 years prior to study enrollment, or individuals who are deemed by the treating investigator to be at low risk for disease recurrence. Additionally, individuals with the following cancers are eligible if diagnosed and curatively treated within the past 2 years: basal or squamous cell carcinomas of the skin, and breast or cervical carcinomas *in situ*. Prostate cancer on observation, with stable PSA for 6 months, is also eligible.

2.8.15 Participants who require ongoing immunosuppressive therapy including systemic corticosteroids (prednisone or equivalent \leq 10 mg daily is permitted). Topical, inhaled, and ophthalmologic steroids are permitted.

2.8.16 Participants with a history of inflammatory bowel disease (e.g. Crohn's disease or ulcerative colitis).

2.8.17 Participants with irritable bowel syndrome (IBS) with greater than 3 loose stools per day at baseline.

2.8.18 Participants with evidence of ongoing systemic bacterial, fungal, or viral infection, except localized fungal infections of the skin or nails. NOTE: participants may be receiving prophylactic antiviral or antibacterial therapies at the treating investigator's discretion. Use of anti-pneumocystis and antiviral prophylaxis is required, see **Section 5.4**.

2.8.19 Participants with a known history of progressive multifocal leukoencephalopathy (PML).

2.8.20 Participants with evidence of chronic active Hepatitis B (HBV, not including patients with prior hepatitis B vaccination or positive serum Hepatitis B antibody), chronic active Hepatitis C infection (HCV), active cytomegalovirus (CMV), or known history of human immunodeficiency virus (HIV):

- If HBc antibody is positive or the patient has a known history of hepatitis B, the subject must be evaluated for the presence of HBV DNA by PCR (see **Appendix B**). Subjects with a known history of hepatitis B and a positive HBc antibody but a negative HBV DNA by PCR are eligible if on suppressive therapy. Subjects with no known history of hepatitis B, with positive HBc antibody and negative HBV DNA by PCR, are eligible but serial monitoring of HBV DNA by PCR is required, see **Section 5.4**. Subjects with positive HBV DNA by PCR are not eligible.
- Participants with positive HBsAg are to be excluded.
- If HCV antibody is positive, the subject must be evaluated for the presence of HCV RNA by PCR. Subjects with positive HCV antibody and negative HCV RNA by PCR are eligible. Subjects with positive HCV RNA by PCR are not eligible.
- If the subject is CMV IgG or CMV IgM positive, the subject must be evaluated for the presence of CMV DNA by PCR. Subjects who are CMV IgG or CMV IgM positive but who are CMV DNA negative by PCR are eligible, anti-viral prophylaxis should be considered per treating investigator discretion.

2.8.21 History of allergic reactions attributed to study drugs including active product or excipients, or compounds of similar chemical or biologic composition to acalabrutinib, umbralisib, or ublituximab, including participants with a history of anaphylaxis (excluding infusion-related reactions) in association with previous anti-CD20 administration.

- 2.8.22 Participants requiring concomitant treatment with any medications or substances that are strong inhibitors or inducers of CYP3A4 at the time of study enrollment. Because the lists of these agents are constantly changing, it is important to regularly consult a frequently-updated medical reference. As part of the enrollment/informed consent procedures, the participant will be counseled on the risk of interactions with other agents, and what to do if new medications need to be prescribed or if the participant is considering a new over-the-counter medicine or herbal product.
- 2.8.23 Participants requiring concomitant treatment with proton pump inhibitors (e.g., omeprazole, esomeprazole, lansoprazole, dexlansoprazole, rabeprazole, or pantoprazole) at the time of study enrollment. Note: participants receiving proton pump inhibitors who switch to H2-receptor antagonists or antacids prior to the first dose of study medication are eligible.
- 2.8.24 Participants with psychiatric illness/social situations that would limit compliance with study requirements.
- 2.8.25 Pregnant women are excluded from this study because acalabrutinib, umbralisib, and ublituximab are anti-cancer agents with the potential for teratogenic or abortifacient effects. Because there is an unknown but potential risk for adverse events in nursing infants secondary to treatment of the mother with acalabrutinib, umbralisib, or ublituximab, breastfeeding must be discontinued prior to the initiation of study treatment. A negative serum pregnancy test is required for women of childbearing potential within 3 days prior to Cycle 1 Day 1.

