2.4.1.2 Infection

Serious infections (bacterial, viral or fungal), including fatal events and opportunistic infections, have been reported in clinical studies with acalabrutinib. The most frequently reported Grade 3 or 4 infection was pneumonia. Across the acalabrutinib clinical development program (including subjects treated with acalabrutinib in combination with other drugs), cases of hepatitis B virus (HBV) reactivation (resulting in liver failure and death in 1 case) and cases of progressive multifocal leukoencephalopathy have occurred in subjects with hematologic malignancies. Monitor patients for signs and symptoms of infection and treat as medically appropriate.

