4.4.2 Hepatitis B Monitoring and Anti-Viral Prophylaxis

All participants are required to have testing for hepatitis B surface antigen (HBsAg) and

hepatitis B core (HBc) antibody at screening. If HBc antibody is positive, the subject must also be evaluated for the presence of hepatitis B viral (HBV) DNA by PCR (see **Appendix B**). Subjects with positive HBc antibody and negative HBV DNA by PCR are eligible, but serial monitoring of HBV DNA is required monthly.

Subjects with a prior history of hepatitis must be closely monitored as clinically indicated based on liver tests and any observed signs/symptoms such as jaundice, abdominal pain, dyspepsia, dark-colored urine often accompanied by lighter-than-normal colored stools, nausea, vomiting or fatigue.

For patients with a prior history of hepatitis B who experience an increase in liver enzymes while on study, hold ublituximab immediately and assess for active hepatitis B infection. If negative for hepatitis B by viral load testing, ublituximab may be resumed. If reactivation of hepatitis B is confirmed, institute hepatitis B antiviral treatment. Ublituximab may be resumed at investigator discretion once hepatitis B infection has resolved, with continued monitoring as described above.

Serious or life-threatening reactivation of viral hepatitis may occur in subjects treated with acalabrutinib or ublituximab. Use of anti-viral prophylaxis will be permitted at the treating investigator's discretion. Entecavir is the preferred agent for pharmacologic prophylaxis. Use of an agent other than entecavir must be discussed with the sponsor-investigator. HBV DNA should be monitored every 1-2 months while a patient is receiving pharmacologic prophylaxis. If the HBV DNA level becomes detectable, all study medications must be discontinued and infectious disease consultation should be obtained. If a patient completes study therapy while taking entecavir, they should remain on entecavir for at least one year after completion of all therapy. If discontinuation of entecavir is considered, patients should have their LFTs and HBV DNA level monitored weekly for the first two months.

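### Sections 2.8.20 and 4.4.2 give opposite entry rules for a participant with known hepatitis B history who is not on suppressive therapy, and neither says whether such therapy continues on study

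*Combined protocol and SAP*

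**What the plan says.** Section 2.8.20 (under 2.8 Exclusion Criteria) sets HBV DNA testing as follows: "If HBc antibody is positive or the patient has a known history of hepatitis B, the subject must be evaluated". It rules out HBsAg-positive people ("Participants with positive HBsAg are to be excluded") and those whose HBV DNA is positive. It then divides the remaining anti-HBc-positive, DNA-negative people by history:

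- Known history: those with "a positive HBc antibody but a negative HBV DNA by PCR are eligible if on suppressive therapy". Serial monitoring is not mentioned for this group.
- No known history: "Subjects with no known history of hepatitis B, with positive HBc antibody and negative HBV DNA by PCR, are eligible", with serial HBV DNA monitoring. For this the text points to Section 5.4, which is 4.4 in the current numbering.

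Section 4.4.2 (Hepatitis B Monitoring and Anti-Viral Prophylaxis) covers the same people in one sentence: "Subjects with positive HBc antibody and negative HBV DNA by PCR are eligible, but serial monitoring of HBV DNA is required monthly". On antivirals it says "Use of anti-viral prophylaxis will be permitted at the treating" investigator's discretion, and it names entecavir as the preferred agent. It also instructs sites to hold ublituximab if liver enzymes rise in a patient with prior hepatitis B, and to discontinue all study medications if HBV DNA becomes detectable.

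**The concern.** Both sections are operative and both use the word eligible, but they attach different conditions to it. A site reading 4.4.2 finds no suppressive-therapy requirement; a site reading 2.8.20 does. The condition in 2.8.20 also speaks only to entry, while 4.4.2, which governs the treatment period, treats HBV antivirals as optional for everyone.

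The protocol treats this risk as serious. Section 2.4.1.2 reports HBV reactivation in the acalabrutinib programme, "resulting in liver failure and death in 1 case", and 4.4.2 warns that viral hepatitis may reactivate severely, even threatening life, under acalabrutinib or ublituximab. As written, whether a known-history participant receives HBV antiviral therapy can depend on which section the site consults.

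**Working it through.** No arithmetic applies, and the plan states no figure on this point to reproduce. The check sets the two sections side by side for a participant who is anti-HBc positive, HBV DNA negative and HBsAg negative.

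| Participant | 2.8.20 | 4.4.2 | Agree? |
|---|---|---|---|
| (a) Known history, on suppressive therapy | Eligible | Eligible, monthly HBV DNA | Yes on entry |
| (b) Known history, not on suppressive therapy | Not eligible | Eligible, monthly HBV DNA | **No** |
| (c) No known history | Eligible, serial HBV DNA | Eligible, monthly HBV DNA | Yes |
| HBV antiviral for known history | Condition of entry; silent afterwards | Discretionary | **Not aligned** |
| HBV DNA monitoring for known history | Not mentioned | Monthly | 2.8.20 silent |

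Reading 2.8.20 as excluding case (b) rests on its contrast between the two groups: the therapy condition is attached to one and left off the other.

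The next step was to look for text elsewhere that settles case (b) or the on-study question.

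- **4.4.1** requires antiviral prophylaxis with umbralisib, but its recommended agents are Valtrex or acyclovir, and footnote 2 of Table 12 describes the requirement as anti-herpetic. It is not presented as HBV suppression; 4.4.2 names entecavir separately.
- **Table 20, footnote h** lists screening tests and refers back to both sections. It does not choose between them. Tables 20 to 23 have no row for serial HBV DNA.
- **Appendix B** interprets serology only.
- **2.8.18** repeats that antiviral prophylaxis is required and points to the same supportive-care section; it does not address HBV history.
- **Continuation.** 4.4.2 says that a patient who finishes study therapy on entecavir should stay on it for at least a year. No sentence addresses whether suppressive therapy that was a condition of entry continues during study treatment.

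Nothing found resolves case (b), and nothing settles continuation.

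For a case (b) participant treated under 4.4.2, three safeguards remain: monthly HBV DNA, the ublituximab hold on an enzyme rise, and the discontinuation rule on detectable DNA. The last is not limited to any subgroup, although it follows the sentence about patients receiving prophylaxis.

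**The case against.** The best answer is that 2.8.20 governs. It is the formal criterion. Section 3.1 requires an investigator to confirm eligibility and a checklist to be completed, the Coordinating Center verifies external sites' documents, and Appendix C 3.5.3 allows no eligibility exception without IRB approval. Section 4.4.2 sits under supportive care, and no text says it relaxes an exclusion. For hepatitis B, 2.8.20 points there only for monitoring of the no-known-history group, and the 4.4.2 sentence closely tracks the rule for that group, so it may be a shortened restatement.

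Much of this stands: a careful site would probably apply 2.8.20 at enrolment. But 4.4.2 declares people eligible without the condition, and it cannot be confined to participants without history, because it gives specific instructions for those with prior hepatitis B. The precedence argument also leaves the on-study question open, since 2.8.20 speaks only to entry.

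A reader might infer more than the documents support:

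- **That this is the highest-risk group.** The documents do not rank HBV risk by known against unknown history. The supportable description is the eligible subgroup for which 2.8.20 sets the stricter condition.
- **That these participants would be unprotected.** They would be without mandated HBV antiviral therapy, but the three safeguards in 4.4.2 remain.
- **That 4.4.2 lets an investigator stop the therapy that allowed entry.** It permits use at discretion and says nothing about withdrawing therapy required at entry. Its entecavir text, which adds weekly checks for two months if stopping is considered, leans the other way.
- **That known-history participants go unmonitored.** The monthly rule in 4.4.2 has no split by history and already covers them.
- **That reactivation would cost evaluable participants.** Section 12.6.2 keeps anyone who received one dose of one agent in the primary analysis.

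**Conclusion.** The contradiction holds for one defined participant: known hepatitis B history, anti-HBc positive, HBV DNA negative, HBsAg negative, not on suppressive therapy. A second gap goes with it: the plan does not say whether suppressive therapy required at entry continues on study.

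The size cannot be stated. The documents do not give the number of anti-HBc-positive participants; the only ceiling is the planned maximum of 60. Sample size, type I error, power and the primary analysis set are unaffected. This is a safety-relevant wording conflict, not a flaw in the statistical design.

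Section 5.5 records that supply of umbralisib and ublituximab ended in March 2023, with participants still on treatment able to continue acalabrutinib. The entry half may therefore have little prospective effect, though the documents do not state that accrual closed. The on-study half still matters for anyone continuing acalabrutinib, which the protocol links to reactivation.

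**What to change.** Reconcile 2.8.20 and 4.4.2, and bring the eligibility checklist (not among the documents) into line, so that:

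1. both sections state the same entry condition for participants with known history and for those without;
2. the text says whether suppressive therapy required at entry is to continue during study treatment, and how that relates to the discretionary wording in 4.4.2;
3. the monitoring wording in 2.8.20 agrees with 4.4.2 for both groups. In the same edit, clarify how the monthly interval relates to the interval of 1 to 2 months that 4.4.2 gives for patients on prophylaxis.

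Which clinical condition stands is the sponsor's decision; this review takes no position on it. The cost is a few sentences in two sections and a checklist line, with no change to the design or analysis.

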2.9 Inclusion of Women and Minorities

Both men and women of all races and ethnic groups are eligible for this trial.

3. REGISTRATION PROCEDURES

3.1 General Guidelines for DF/HCC Institutions

Institutions will register eligible participants in the Clinical Trials Management System (CTMS) OnCore. Registrations must occur prior to the initiation of any protocol-specific therapy or intervention. Any participant not registered to the protocol before protocol-specific therapy or intervention begins will be considered ineligible and registration will be denied.

An investigator will confirm eligibility criteria and a member of the study team will complete the protocol-specific eligibility checklist.

Following registration, participants may begin protocol-specific therapy and/or intervention. Issues that would cause treatment delays should be discussed with the Principal Investigator (PI) of the registering site. If the subject does not receive protocol therapy following

registration, the subject must be taken off study in the CTMS (OnCore) with an appropriate date and reason entered.

3.2 Registration Process for DF/HCC Institutions

Applicable DF/HCC policy (REGIST-101) must be followed.

3.3 General Guidelines for Other Investigative Sites

Eligible participants will be entered on study centrally at the Dana-Farber Cancer Institute by the Study Coordinator or Project Manager. The required forms can be found in **Section 4.4**.

Following registration, participants should begin protocol therapy within 5 days. Issues that would cause treatment delays should be discussed with the Principal Investigator (PI). If the subject does not receive protocol therapy following registration, the subject must be taken off-study in the CTMS (OnCore) with an appropriate date and reason entered.

3.4 Registration Process for Other Investigative Sites

To register a participant, the following documents should be completed by the participating site and e-mailed to the Study Coordinator/Project Manager:

- Signed participant consent form
- HIPAA authorization form
- DFCI eligibility checklist
- Screening provider note including the medical/surgical history, ECOG performance status, vital signs, and physical exam findings
- Copies of laboratory reports and clinical information confirming satisfaction of eligibility criteria.

The participating site will then e-mail the Study Coordinator or Project Manager to verify eligibility. The Study Coordinator/Project Manager will follow DF/HCC policy (REGIST-101) and register the participant on the protocol. The Study Coordinator/Project Manager will e-mail the participant study number, and if applicable the dose treatment level, to the participating site. The Study Coordinator/Project Manager may also contact the participating site and verbally confirm registration

NOTE: Registration can only be conducted during the regular business hours of 8:30 AM to 4:30 PM Eastern Standard Time Monday through Friday, holidays excluded. Same day treatment registrations will only be accepted with prior notice and discussion with the DF/HCC Project Manager or Study Coordinator.

4. TREATMENT PLAN

4.1 Treatment Regimen

A treatment cycle is defined as 28 consecutive days. Treatment will be administered on an outpatient basis. Reported adverse events and potential risks are described in **Section 7**. Appropriate dose modifications are described in **Section 6**.

Participants will receive acalabrutinib at the FDA approved dose of 100 mg by mouth twice daily and umbralisib at 800 mg by mouth once daily continuously throughout each treatment cycle. Ublituximab will be given IV starting with cycle 7 on days 1, 2, 8, and 15 and cycles 8-12 on day 1.

Participants who are in bone marrow and CT confirmed CR at the end of cycle 12 will stop dosing with acalabrutinib and umbralisib.. Participants not in CR will continue to cycles 13-24.

Participants will have peripheral blood monitoring for MRD as described in the **Study Calendar** in **Section 10**. If early relapse or recurrence is detected, the patient will undergo restaging with a CT scan and a bone marrow biopsy / aspirate. At the discretion of the treating investigator, patients with early relapse not meeting iwCLL criteria for retreatment may resume dosing with acalabrutinib and umbralisib until further disease progression, unacceptable toxicity, or other criteria are met as described in **Section 5.5**. The study agents will be resumed at the dose levels the participant was receiving prior to discontinuation. Dosing will resume for a maximum of 12 additional treatment cycles, such that participants may receive a maximum total of 36 cycles of study therapy.

Table 4: Regimen Description

Agent	Premedications; Precautions	Dose	Route	Schedule ¹	Cycle Length
Acalabrutinib	May be taken with or without food.	100 mg	By mouth	Twice Daily	
Umbralisib	Take within 30 minutes of a meal. Participants are required to receive prophylactic anti-viral and anti-pneumocystis jiroveci pneumonia (PJP) treatment, refer to Section 5.4 .	800 mg	By mouth	Once Daily	28 days

Table 4: Regimen Description

Agent	Premedications; Precautions	Dose	Route	Schedule ¹	Cycle Length
Ublituximab	
Pre-medicate with an antihistamine (diphenhydramine 50 mg or equivalent) and a corticosteroid (dexamethasone 10 – 20 mg or methylprednisolone 80 mg or equivalent).^{2,3,4}
 
 • If oral pre-medication: start the ublituximab infusion 45 – 60 minutes after the ingestion of the oral pre-medications • If IV pre-medication: start the ublituximab infusion 30 – 35 minutes after the completion of the last pre-medication infusion 	See Section 5.3.3	IV	
Cycle 7: Days 1, 2, 8, 15
 
Cycles 8 – 12: Day 1
	

 1. Order of administration of the study agents does not matter. 2. Diphenhydramine must be 50 mg IV on Cycle 7 day 1 and 2, but may be reduced to 25 mg on subsequent infusions in the absence of infusion related reactions and at treating physician discretion. After the completion of cycle 8, use of corticosteroid pre-medication may be discontinued with approval from the sponsor-investigator if the participant has not experienced any infusion-related or hypersensitivity reactions. 3. Administration of oral acetaminophen 650 mg (or equivalent) may be as clinically warranted, or in participants who experience fever/pyrexia after the first infusion. 4. Infusion-related hypotension may occur, investigators should consider holding anti-hypertensive medications 12-24 hours prior to and throughout the infusion. Decision to withhold anti-hypertensive medication is at the treating investigator's discretion. 					

